### Contraception Requirements

#### Male Participants:

Male participants with female partners of childbearing potential are eligible to participate if they agree to one of the following during the protocol defined time frame in section 6.1:

- Be abstinent from penile-vaginal intercourse as their usual and preferred lifestyle (abstinent on a long term and persistent basis) and agree to remain abstinent
- Use a male condom plus partner use of a contraceptive method with a failure rate of <1% per year as described in [Table 10](#) when having penile-vaginal intercourse with a woman of childbearing potential who is not currently pregnant.
  - Note: Men with a pregnant or breastfeeding partner must agree to remain abstinent from penile-vaginal intercourse or use a male condom during each episode of penile penetration.

### Female Participants:

Female participants of childbearing potential are eligible to participate if they agree to use one of the contraception methods described in [Table 10](#) consistently and correctly during the protocol-defined time frame in Section 6.1.

Table 10 Contraceptive Methods

Acceptable Contraceptive Methods Failure rate of >1% per year when used consistently and correctly.

• Male or female condom with or without spermicide

• Cervical cap, diaphragm or sponge with spermicide

Highly Effective Contraceptive Methods That Are User Dependent a Failure rate of <1% per year when used consistently and correctly.

• Combined (estrogen- and progestogen- containing) hormonal contraception b

◦ Oral

◦ Intravaginal

◦ Transdermal

◦ Injectable

• Progestogen-only hormonal contraception b

◦ Oral

◦ Injectable

Highly Effective Methods That Have Low User Dependency Failure rate of <1% per year when used consistently and correctly.

• Progestogen- only contraceptive implant b, c

• Intrauterine hormone-releasing system (IUS) b

• Intrauterine device (IUD)

• Bilateral tubal occlusion

 
• Vasectomized partner
 
A vasectomized partner is a highly effective contraception method provided that the partner is the sole male sexual partner of the WOCBP and the absence of sperm has been confirmed. If not, an additional highly effective method of contraception should be used.
 
• Sexual abstinence
 
Sexual abstinence is considered a highly effective method only if defined as refraining from heterosexual intercourse during the entire period of risk associated with the study treatment. The reliability of sexual abstinence needs to be evaluated in relation to the duration of the study and the preferred and usual lifestyle of the participant.)

Notes:

Use should be consistent with local regulations regarding the use of contraceptive methods for participants of clinical studies.

- a) Typical use failure rates are higher than perfect-use failure rates (i.e. when used consistently and correctly).
- b) If hormonal contraception efficacy is potentially decreased due to interaction with study treatment, condoms must be used in addition to the hormonal contraception during the treatment period and for at least 120 days, corresponding to time needed to eliminate study treatment plus 30 days for study treatments with genotoxic potential, after the last dose of study treatment.
- c) If locally required, in accordance with Clinical Trial Facilitation Group (CTFG) guidelines, acceptable hormonal contraceptives are limited to those which inhibit ovulation.

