## Demographics

Male participants:

9. A male participant must agree to use a contraception, and refrain from donating sperm, as detailed in Appendix 5 of this protocol during the treatment period and for at least 120 days, corresponding to time needed to eliminate any study treatments (MK-7162 and pembrolizumab), after the last dose of study treatment.

Female participants:

10. A female participant is eligible to participate if she is not pregnant (Appendix 5), not breastfeeding, and at least one of the following conditions applies: A woman of childbearing potential (WOCBP) who agrees to follow the contraception guidance in Appendix 5 during the treatment period for at least 120 days (corresponding to time needed to eliminate any study treatment(s) (MK-7162 and pembrolizumab).

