#### 6.3.2 Contraception

MK-7162 and pembrolizumab may have adverse effects on a fetus in utero. Furthermore, it is not known if MK-7162 or pembrolizumab have transient adverse effects on the composition of sperm.

For this study, male participants will be considered to be of non-reproductive potential if they have azoospermia (whether due to having had a vasectomy or due to an underlying medical condition).

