## 12.5 Appendix 5: Contraceptive Guidance and Pregnancy Testing

### Woman of Childbearing Potential (WOCBP)

A woman is considered fertile following menarche and until becoming post-menopausal unless permanently sterile (see below)

Women in the following categories are not considered WOCBP:

- Premenarchal
- Premenopausal female with 1 of the following:
  - Documented hysterectomy
  - Documented bilateral salpingectomy
  - Documented bilateral oophorectomy

Note: Documentation can come from the site personnel's review of the participant's medical records, medical examination, or medical history interview.

- Postmenopausal female
  - A postmenopausal state is defined as no menses for 12 months without an alternative medical cause.
    - A high follicle stimulating hormone (FSH) level in the postmenopausal range may be used to confirm a postmenopausal state in women not using hormonal contraception or hormonal replacement therapy (HRT). However, in the absence of 12 months of amenorrhea, confirmation with two FSH measurements in the postmenopausal range is required.
  - Females on HRT and whose menopausal status is in doubt will be required to use one of the non-hormonal highly effective contraception methods if they wish to continue their HRT during the study. Otherwise, they must discontinue HRT to allow confirmation of postmenopausal status before study enrollment.

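### Appendix 5 accepts a single barrier method for a treated woman of childbearing potential, yet asks for a <1% per year method in two other groups, and gives no reason for the looser rule

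*Combined protocol and SAP*

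**What the plan says.** Inclusion criterion 10 (Section 6.1) admits "A woman of childbearing potential (WOCBP) who agrees to follow the contraception guidance in Appendix 5 during the treatment period" and names no method of its own, so the operative rule is in Appendix 5 (Section 12.5). Under Female Participants it reads: "Female participants of childbearing potential are eligible to participate if they agree to use one of the contraception methods described in" Table 10.

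Table 10 has three tiers. The first, headed as acceptable methods, carries a >1% per year failure label. It holds "Male or female condom with or without spermicide" and the cap, diaphragm or sponge used with spermicide. The other two tiers, both headed as highly effective, carry a <1% label. All the labels assume consistent and correct use.

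Two other rules in Appendix 5 set a higher minimum:

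- A male participant who is not abstinent must "Use a male condom plus partner use of a contraceptive method with a failure rate of <1% per year" when his partner is of childbearing potential and not currently pregnant. A note relaxes this for some partners: "Men with a pregnant or breastfeeding partner must agree to remain abstinent from penile-vaginal intercourse or use a male condom".
- For women on HRT of uncertain menopausal status, the rule is that they "will be required to use one of the non-hormonal highly effective contraception methods if they wish to continue their HRT during the study". The alternative is to stop HRT so that their status can be established.

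On risk, Section 6.3.2 says that "MK-7162 and pembrolizumab may have adverse effects on a fetus in utero", and that "it is not known if MK-7162 or pembrolizumab have transient adverse effects on the composition of sperm".

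**The concern.** The woman who takes both drugs can meet the eligibility rule with a condom alone. For the untreated, not-currently-pregnant partner of a male participant, the same appendix treats a condom alone as too little. It also asks more of a treated woman whose fertility is in doubt and who stays on HRT than of a treated woman known to be fertile. The only risk statement in the body of the protocol does not explain this ordering: it names a possible fetal effect of both drugs, and for sperm says only that an effect is unknown.

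What is at stake is participant and fetal safety at the point of eligibility. The other safeguards do not set a minimum method. Exclusion criterion 15 concerns the intention to conceive. After the negative test required within 72 hours before the first dose (Section 6.2, criterion 17, and Section 9.5.4.2), the Schedule of Activities has no pregnancy test until End of Treatment. In between, Appendix 5 requires a test after a missed menstrual cycle or on suspicion, and other testing is optional or local. Those tests, and the immediate stop of treatment in Section 6.3.3, act only once exposure may already have occurred.

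**Working it through.** The plan states no figure to reproduce, so the check is a comparison of the rules.

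| Group | Takes study drug | Minimum method | Source |
|---|---|---|---|
| Female participant of childbearing potential | Yes | Any one Table 10 method, including one barrier method labelled >1% per year | Appendix 5, Female Participants; Table 10 |
| Partner of a non-abstinent male participant, of childbearing potential and not currently pregnant | No | Male condom plus a <1% partner method | Appendix 5, Male Participants |
| Pregnant or breastfeeding partner of a male participant | No | Abstinence or male condom | Appendix 5, Male Participants, note |
| Female participant on HRT, menopausal status in doubt, HRT continued | Yes | Non-hormonal highly effective method | Appendix 5, definition of childbearing potential |

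**Does anything else raise the first row?**

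1. Criterion 10 only refers back to Appendix 5.
2. Table 10 footnote b adds condoms when a hormonal method may be weakened by interaction with study treatment. It does not reach a woman who uses only a barrier method.
3. The note under Table 10 defers to local regulations. These may be stricter at some sites, but the protocol itself sets no minimum through that note.

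So the barrier-only option stands.

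**Can a size be put on it?** The only rate in the documents is the 1% per year line between the tiers. Carried over the longest course plus 120 days:

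- 36 × 21 + 120 = 876 days, and 876 / 365.25 = 2.40 years
- 1 − (1 − 0.01)^2.40 = 2.4%

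For a woman who stops after the 42-day DLT window:

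- 42 + 120 = 162 days = 0.44 years
- 1 − (1 − 0.01)^0.44 = 0.44%

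These values are the floor for the barrier tier and the ceiling for the <1% tiers. They therefore do not measure the difference between the tiers or the benefit of a change. They also depend on counting 120 days after the last dose. Criterion 9 (men) and footnote b say that in words. Criterion 10 (women) mentions 120 days without saying that they follow the last dose. The reading is reasonable, but it is an interpretation.

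**The case against.** The strongest answer is that this is a deliberate choice. The lower tier is openly labelled, and the female rule covers the whole table. Whether that tier is good enough depends on reproductive-toxicity and interaction data, which the protocol leaves to the Investigator's Brochures. Section 6.3.2 says only that harm is possible and gives no degree.

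The comparison groups also differ. Participants have pregnancy tests, while none is scheduled for a male participant's partner. A missed cycle is a poor trigger for testing in a woman on HRT of doubtful menopausal status. Either could justify a stricter rule. The appendix does not treat 1% as a floor for everyone, since a condom alone is accepted for a breastfeeding partner. Moving to the <1% tiers would still admit user-dependent pills, and footnote a says that typical use fails more often than perfect use.

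Much of this stands. A reader might infer that barrier methods are unsafe with these drugs, or that a known number of pregnancies would follow. The documents support neither: the Brochures are not available here, and the 1% boundary gives no difference between tiers. Nor do they support reading the rule as a breach of a universal 1% standard.

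The testing-based explanations, however, appear nowhere in the protocol. They also do not show why a woman known to be fertile should have a looser rule than one whose fertility is uncertain, because testing detects a pregnancy only after it has begun.

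**Conclusion.** The concern holds as an unexplained asymmetry. A treated woman of childbearing potential may enrol on one barrier method labelled >1% per year, while the same appendix asks for a <1% method in two other defined groups. The protocol's own risk statement gives no reason for the difference.

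No magnitude is attached. The conclusion rests on the wording of Appendix 5, criterion 10 and Section 6.3.2 alone, and the toxicity data could support a different choice.

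Reach is uncertain. The stated purpose of Amendment 02 is to let the study close, and with no further enrolment the point has no practical effect. Part B, estimated in Section 5.2 at 150 further participants of both sexes, would need its own amendment, and the documents do not say how many would be women of childbearing potential.

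The mTPI design, the sample size and the analyses are untouched. This is a low-priority, inexpensive improvement to consider.

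**What to change.** For any further enrolment, including Part B, make two edits in Appendix 5:

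1. In the female rule, replace the reference to any one Table 10 method with: one of the highly effective (<1% per year) methods in Table 10.
2. Mark the barrier tier of Table 10 as usable only in addition to one of those methods.

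Leave the male rule, the HRT rule and the local-regulations note as they are, and bring the consent text into line.

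The cost falls on recruitment. Some candidates would have to change or add a method within the screening phase of up to 28 days, and a few might be delayed or not enrol. Among the non-hormonal <1% options, an IUD or tubal occlusion needs a procedure, a vasectomized partner needs confirmed absence of sperm, and abstinence has to be judged against the participant's usual lifestyle. Hormonal options such as oral contraception need no procedure. No visits, tests or analyses are added.

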## **Pregnancy Testing**

WOCBP should only be included after a negative highly sensitive urine or serum pregnancy test.

Pregnancy testing will be performed whenever an expected menstrual cycle is missed or when pregnancy is otherwise suspected.

## **12.6 Appendix 6: Collection and Management of Specimens for Future Biomedical Research**

### **1. Definitions**

- a. Biomarker: A biological molecule found in blood, other body fluids, or tissues that is a sign of a normal or abnormal process or of a condition or disease. A biomarker may be used to see how well the body responds to a treatment for a disease or condition.
- b. Pharmacogenomics: The investigation of variations of DNA and RNA characteristics as related to drug/vaccine response.
- c. Pharmacogenetics: A subset of pharmacogenomics, pharmacogenetics is the influence of variations in DNA sequence on drug/vaccine response.
- d. DNA: Deoxyribonucleic acid.
- e. RNA: Ribonucleic acid.

### **2. Scope of Future Biomedical Research**

The specimens consented and/or collected in this trial as outlined in Section 9.8 – Future Biomedical Research Samples will be used in various experiments to understand:

- o The biology of how drugs/vaccines work
- o Biomarkers responsible for how a drug/vaccine enters and is removed by the body
- o Other pathways drugs/vaccines may interact with
- o The biology of disease

The specimen(s) may be used for future assay development and/or drug/vaccine development.

It is now well recognized that information obtained from studying and testing clinical specimens offers unique opportunities to enhance our understanding of how individuals respond to drugs/vaccines, enhance our understanding of human disease and ultimately improve public health through development of novel treatments targeted to populations with the greatest need. All specimens will be used by the Sponsor or those working for or with the Sponsor.

### **3. Summary of Procedures for Future Biomedical Research**

#### **a. Participants for Enrollment**

All participants enrolled in the clinical trial will be considered for enrollment in the Future Biomedical Research sub-trial.

#### **b. Informed Consent**

Informed consent for specimens (i.e., DNA, RNA, protein, etc.) will be obtained during screening for protocol enrollment from all participants or legal guardians, at a trial visit by the investigator or his or her designate. Informed consent for Future Biomedical Research should be presented to the participants on the visit designated in the trial flow chart. If delayed, present consent at next possible Participant Visit.

Consent forms signed by the participant will be kept at the clinical trial site under secure storage for regulatory reasons.

A template of each trial site's approved informed consent will be stored in the Sponsor's clinical document repository.

c. eCRF Documentation for Future Biomedical Research Specimens

Documentation of participant consent for Future Biomedical Research will be captured in the electronic Case Report Forms (eCRFs). Any specimens for which such an informed consent cannot be verified will be destroyed.

d. Future Biomedical Research Specimen(s)

Collection of specimens for Future Biomedical Research will be performed as outlined in the trial flow chart. In general, if additional blood specimens are being collected for Future Biomedical Research, these will usually be obtained at a time when the participant is having blood drawn for other trial purposes.

**4. Confidential Participant Information for Future Biomedical Research**

In order to optimize the research that can be conducted with Future Biomedical Research specimens, it is critical to link participant' clinical information with future test results. In fact little or no research can be conducted without connecting the clinical trial data to the specimen. The clinical data allow specific analyses to be conducted. Knowing participant characteristics like gender, age, medical history and treatment outcomes are critical to understanding clinical context of analytical results.

To maintain privacy of information collected from specimens obtained for Future Biomedical Research, the Sponsor has developed secure policies and procedures. All specimens will be single-coded per ICH E15 guidelines as described below.

At the clinical trial site, unique codes will be placed on the Future Biomedical Research specimens. This code is a random number which does not contain any personally identifying information embedded within it. The link (or key) between participant identifiers and this unique code will be held at the trial site. No personal identifiers will appear on the specimen tube.

**5. Biorepository Specimen Usage**

Specimens obtained for the Sponsor will be used for analyses using good scientific practices. Analyses utilizing the Future Biomedical Research specimens may be performed by the Sponsor, or an additional third party (eg, a university investigator) designated by the Sponsor. The investigator conducting the analysis will follow the Sponsor's privacy and confidentiality requirements. Any contracted third party analyses will conform to the specific scope of analysis outlined in this sub-trial. Future Biomedical Research specimens remaining with the third party after specific analysis is performed will be reported to the Sponsor.

## 6. Withdrawal From Future Biomedical Research

Participants may withdraw their consent for Future Biomedical Research and ask that their biospecimens not be used for Future Biomedical Research. Participants may withdraw consent at any time by contacting the principal investigator for the main trial. If medical records for the main trial are still available, the investigator will contact the Sponsor using the designated mailbox ([contact]). Subsequently, the participant's specimens will be flagged in the biorepository and restricted to main study use only. If specimens were collected from study participants specifically for Future Biomedical Research, these specimens will be removed from the biorepository and destroyed. Documentation will be sent to the investigator confirming withdrawal and/or destruction, if applicable. It is the responsibility of the investigator to inform the participant of completion of the withdrawal and/or destruction, if applicable. Any analyses in progress at the time of request for withdrawal/destruction or already performed prior to the request being received by the Sponsor will continue to be used as part of the overall research trial data and results. No new analyses would be generated after the request is received.

In the event that the medical records for the main trial are no longer available (eg, if the investigator is no longer required by regulatory authorities to retain the main trial records) or the specimens have been completely anonymized, there will no longer be a link between the participant's personal information and their specimens. In this situation, the request for withdrawal of consent and/or destruction cannot be processed.

## 7. Retention of Specimens

Future Biomedical Research specimens will be stored in the biorepository for potential analysis for up to 20 years from the end of the main study. Specimens may be stored for longer if a regulatory or governmental authority has active questions that are being answered. In this special circumstance, specimens will be stored until these questions have been adequately addressed.

Specimens from the trial site will be shipped to a central laboratory and then shipped to the Sponsor-designated biorepository. If a central laboratory is not utilized in a particular trial, the trial site will ship directly to the Sponsor-designated biorepository. The specimens will be stored under strict supervision in a limited access facility which operates to assure the integrity of the specimens. Specimens will be destroyed according to Sponsor policies and procedures and this destruction will be documented in the biorepository database.

## 8. Data Security

Databases containing specimen information and test results are accessible only to the authorized Sponsor representatives and the designated trial administrator research personnel and/or collaborators. Database user authentication is highly secure, and is accomplished using network security policies and practices based on international standards to protect against unauthorized access.

## **9. Reporting of Future Biomedical Research Data to Participants**

No information obtained from exploratory laboratory studies will be reported to the participant, family, or physicians. Principle reasons not to inform or return results to the participant include: Lack of relevance to participant health, limitations of predictive capability, and concerns regarding misinterpretation.

If important research findings are discovered, the Sponsor may publish results, present results in national meetings, and make results accessible on a public website in order to rapidly report this information to doctors and participants. Participants will not be identified by name in any published reports about this study or in any other scientific publication or presentation.

